12.9 Subgroup Analyses

The ITT population, defined as the set of all patients randomized to treatment, will be analyzed and presented for the Primary Endpoint. The same analyses will be conducted on the PP population, defined as those patients who are randomized, receive MP as defined in the protocol, and have no protocol violations preventing analysis (e.g. – post-op patients who receive steroids off-protocol). A two-sided test with alpha of 0.05 will be used. The following subgroups will be analyzed for the Primary Endpoint:

Underlying diagnosis:	Palliated vs. Corrective procedure
Age:	≤ 7 days vs. 8-31 days
Body weight:	≤ 2.5 kg vs. > 2.5 kg

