3.2 Exclusion Criteria

Patients who meet any of these criteria are not eligible for enrollment as study participants

- Prematurity: < 37 weeks post gestational age at time of surgery
- Treatment with intravenous steroids within the two days prior to scheduled surgery.
- Participation in research studies involving the evaluation of investigational drugs or vaccines within 30 days of randomization.
- Suspected infection that would contraindicate steroid use (e.g. – Herpes)
- Known hypersensitivity to IVMP or one of its components or other contraindication to steroid therapy (e.g. - gastrointestinal bleeding).
- Preoperative use of mechanical circulatory support or active resuscitation at the time of proposed randomization.
- Inability to comply with study procedures.

4 Study Design

This is a multi-center, prospective, randomized, double blind, placebo controlled study of intraoperative MP in neonates undergoing CPB. Patients will be allocated to one of the 2 study groups in the ratio of 1:1. The randomization will be stratified by corrective vs. palliative surgery and by surgeon. The Primary Endpoint is a composite morbidity-mortality outcome, evaluated as intention to treat (ITT). Secondary endpoints include inotropic score, incidence of LCOS, fluid balance, ICU stay parameters, levels of inflammatory markers, safety parameters, and neurodevelopmental outcomes at 1 year. A two-sided test with a type I error rate of 0.05 will be used for all endpoints with no adjustments of the p-value for multiple testing.

It is expected that 190 patients (95 patients per treatment arm) will be needed to be enrolled in the study to show a significant difference between groups. The annual amount of eligible & consenting patients at MUSC for this trial and a similar trial over 3 years was 35 cases/year. The annual amount of eligible patients at Children's Healthcare of Atlanta based on the surgical volume in 2012 would be 74 neonates. Anticipating a 70% consent rate would result in 50 cases a year. As such, this study would expect to reach the goal of 190 evaluable subjects in 4 years, within the 5 year proposed grant cycle.

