12.3 Subgroup Analyses

The modified ITT population, defined as the set of all patients randomized to treatment and underwent cardiopulmonary bypass, will be analyzed and presented for the Primary Endpoint. The same analyses will be conducted on the PP population, defined as those patients who are randomized, receive study drug as defined in the protocol, and have no major protocol violations preventing analysis (e.g. – post-op patients who receive steroids off-protocol). A two-sided test

with alpha of 0.05 will be used. The following subgroups will be analyzed for the Primary Endpoint:

Underlying diagnosis:	Palliated vs. Corrective procedure
Age:	≤ 7 days vs. >7 days
Body weight:	≤ 2.5 kg vs. >2.5 kg

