12.7 Sample Size and Power Calculation For Primary Endpoint

Using data from the previous steroid study performed by [name] the incidence of a similar composite endpoint occurred in 33% of the subjects. This proposed study is powered to detect an absolute difference of 20% between groups. Enrollment of 190 patients (95 per treatment group) will be required to provide 80% power to detect this difference between groups, with an experiment-wise alpha of 0.05 (two-sided), allowing for 1 interim look at the data to assess for superiority and futility. The power analysis was performed using Cytel's East software package (Cambridge, MA) and assumes an O'Brien Fleming alpha spending function.

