12.10 Statistical Methods

Descriptive statistics will be used to characterize the two treatment groups with respect to demographics and baseline clinical characteristics. T-tests, chi-square tests, and non-parametric statistical tests will be used, as appropriate, to compare the groups at baseline. Any significant imbalances will be accounted for in the analyses using multivariable techniques. The primary intention-to-treat analysis comparing the composite outcome between treatment groups will be conducted using generalized linear model. The primary analysis will be adjusted for underlying diagnosis and surgeon. Logistic regression models will be used for the per-protocol analysis and for analyses of secondary categorical outcomes. For continuous variables such as change from baseline in vital signs, hematology, and clinical chemistry parameters, analysis of covariance (ANCOVA) will be utilized with the baseline value used as covariates. Unless otherwise stated, baseline is defined as the last observation before the administration of the study drug. Time to event data (duration of mechanical ventilation, length of ICU stay, and length of hospitalization) will be assessed via non-parametric log-rank tests.

Once half of the study subjects have been recruited and assessed, an interim analysis will also be conducted and presented to the DSMB, for which the p-value thresholds for stopping the study for superiority or futility will be 0.003 and 0.72, respectively. The p-value used at the end of the study with full enrollment will be 0.049, preserving an experimentwise 2-sided alpha level of 0.05. These stopping thresholds are based on an O'Brien-Fleming alpha spending function. For an additional level of safety oversight, the PI will place enrollment on temporary hold if 1 year mortality exceeds 35.5% and the DSMB will be asked to provide an expedited data safety review, concluding with next step recommendations. All analyses will be conducted in SAS v9.2 (Cary, NC).

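### The subgroup sections state a 0.05 test but no treatment-by-subgroup interaction test, so chance differences between levels could be read as effect modification

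*Combined protocol and SAP*

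**What the plan says.** Section 12.9 first describes the ITT and per-protocol analyses of the primary endpoint. It continues: "A two-sided test with alpha of 0.05 will be used. The following subgroups will be analyzed for the Primary Endpoint". The factors are "Palliated vs. Corrective procedure", age "≤ 7 days vs. 8-31 days" and body weight "≤ 2.5 kg vs. > 2.5 kg". Section 12.3 has the same sequence, ending in "The following subgroups will be analyzed for the Primary Endpoint", with the same three factors.

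Section 4 (Study Design) says that a two-sided 0.05 test "will be used for all endpoints with no adjustments of the p-value for multiple testing".

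The methods text (12.4 and 12.10) names a generalized linear model for the primary comparison and says: "The primary analysis will be adjusted for underlying diagnosis and surgeon". Those are main-effect adjustments. They do not ask whether the methylprednisolone effect differs by diagnosis. The other methods named are logistic regression, ANCOVA, log-rank tests and correlation analyses. The documents contain no treatment-by-subgroup term, no exploratory label for the subgroups, and no rule for interpreting them.

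**The concern.** A test within one level asks whether there is an effect in that level. It does not ask whether the effect differs between levels, which is the usual reason for looking at subgroups. The trial has about 80% power in the whole sample, so each level is underpowered. A split verdict (p below 0.05 in one level, above it in the other) is therefore an ordinary chance result when the effect is the same everywhere.

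At stake is the reporting of the primary endpoint by subgroup. The trial could suggest that the drug works only in corrective surgery, or only in older neonates, when nothing differs. It could also draw a positive subgroup from an overall null result.

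**Working it through.** **Inputs from the documents.** 95 per arm, 80% power, a 20-point absolute difference and two-sided 0.05 (12.1 and 12.7). For the event rate: "the incidence of a similar composite endpoint occurred in 33% of the subjects". Three two-level factors (12.3 and 12.9).

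**Assumptions.** The direction of the 20 points is not stated; I take 53% vs 33%. The documents give no subgroup splits; I take 50/50 for procedure, 50/50 for age and 15/85 for weight. Factors are independent of each other and of baseline risk, and the model is unadjusted.

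**1. The plan's own figure.** Power = Φ{(|Δ|√n − 1.96√[2p̄(1−p̄)]) / √v}, with p̄ = 0.43 and v = 0.53×0.47 + 0.33×0.67 = 0.4702. At n = 95: (1.949 − 1.372)/0.686 = 0.84, so power is 80.0%. The stated size is reproduced.

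**2. One half of the sample.** At n = 47.5 per arm: (1.378 − 1.372)/0.686 ≈ 0.01, so power is 50.4%.

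**3. Discordance under a uniform effect.** If the two levels have powers P and Q, discordance = P(1−Q) + Q(1−P).
- 50/50 factor: 2 × 0.504 × 0.496 = 50%.
- 20/80 factor (powers 0.233 and 0.706): 61%.
- 10/90 factor (powers 0.135 and 0.757): 69%.

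**4. No effect.** Six independent 0.05 tests give 1 − 0.95⁶ = 26.5%. The six tests share the same patients, so the true figure is lower and needs simulation.

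**5. Simulation.** 20,000 trials per scenario, 95 per arm, pooled z-tests within levels, Wald interaction tests on the risk-difference scale.

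| Scenario | Level tests | Interaction tests |
|---|---|---|
| Uniform 53% vs 33%, one 50/50 factor | discordant in 50% | false signal in about 5% |
| Uniform 53% vs 33%, any of three factors | discordant in 82% | false signal in 17% |
| No effect (43% in both arms), any signal | at least one of six significant in 22% | at least one of three significant in 16–17% |

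In 17% of the no-effect trials a level test is significant while the overall result is not. The 15/85 factor alone gives about 7% false interaction signals on the risk-difference scale. On the log-odds scale the any-of-three rate under the uniform effect is 12–14%.

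**6. Sensitivity.** With the small-weight share varied from 10% to 50%, discordance for at least one factor is 74–83%. With 33% vs 13% or 43% vs 23% in place of 53% vs 33%, an evenly split factor is discordant in about 46% or 49% of trials.

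**7. Power of the interaction test.** For a 20-point difference in effect on a 50/50 factor, SE = √(4 × 0.4702/95) = 0.141. Power ≈ Φ(0.20/0.141 − 1.96) = Φ(−0.54) ≈ 30%. It is about 21% for a 20/80 factor and 13% for a 10/90 factor.

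**The case against.** The plan says only that the subgroups will be analysed. It does not order separate tests within levels and does not exclude an interaction term. Writing the factors as contrasts is compatible with comparing levels. The 0.05 sentence follows the ITT and per-protocol text and may govern those analyses. An interaction test would carry the same alpha, so the alpha does not identify the test. Section 12.11 also mentions a subsequent SAP. All of this stands. A reader might infer that the plan mandates six within-level tests and rejects interaction testing; the documents do not support that. What remains is that no subgroup method is stated beyond the 0.05 level, and the text leads most naturally to level-by-level tests.

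Nor do the documents say how subgroup results would be interpreted. That chance differences *would* be reported as real is an inference; *could* is as far as the text goes.

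A reader might also set 82% (any of three factors) against 5% (one interaction test on one factor). That is not like for like; the comparison is 82% against 17%. With no effect, three unadjusted interaction tests cut false signals only from about 22% to 17%.

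Finally, the factors are few and pre-specified, and procedure type is a stratification factor. This limits the problem, but the rates above already assume only three factors.

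**Conclusion.** The concern holds as a gap in the stated method: a 0.05 level, no multiplicity adjustment, no interaction test and no exploratory label. If the test is applied within levels, a uniform effect would produce a split verdict in about half of trials for an evenly split factor, and in about 82% for at least one of the three. Interaction tests would give a false signal in about 5% and 17%. The advantage is large when there is a real uniform effect and modest when there is none.

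The exact rates depend on the assumed splits and on 53% vs 33%. The conclusion does not: discordance stays common across the splits and effect sizes tried. It would be going too far to say that the trial's main result is at risk. The primary test, sample size and stopping rules are untouched.

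**What to change.** In both 12.3 and 12.9:

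- Keep the 0.05 sentence, and tie it explicitly to the ITT/modified ITT and per-protocol analyses.
- For the subgroups, add one treatment-by-factor interaction term per factor to the primary model, fitted one factor at a time. State the model's link and the effect scale, because 12.4 and 12.10 name neither and interaction depends on scale when baseline risk differs between levels.
- Report the effect in each level with a 95% confidence interval, and make no level-specific significance claims.
- Label the subgroup analyses exploratory, including the three unadjusted interaction tests.

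The cost is a few sentences and three model fits, with no change to sample size, data collection or conduct. The downside is low interaction power (about 30% for a 20-point difference in effect on a 50/50 factor), so real effect modification may be missed and subgroup claims will be weaker.

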12.10 Statistical Methods

Descriptive statistics will be used to characterize the two treatment groups with respect to demographics and baseline clinical characteristics. T-tests, chi-square tests, and non-parametric statistical tests will be used, as appropriate, to compare the groups at baseline. Any significant imbalances will be accounted for in the analyses using multivariable techniques. The primary intention-to-treat analysis comparing the composite outcome between treatment groups will be conducted using generalized linear model. The primary analysis will be adjusted for underlying diagnosis and surgeon. Logistic regression models will be used for the per-protocol analysis and for analyses of secondary categorical outcomes. For continuous variables such as change from baseline in vital signs, hematology, and clinical chemistry parameters, analysis of covariance (ANCOVA) will be utilized with the baseline value used as covariates. Unless otherwise stated, baseline is defined as the last observation before the administration of the study drug. Time to event data (duration of mechanical ventilation, length of ICU stay, and length of hospitalization) will be assessed via non-parametric log-rank tests.

Once half of the study subjects have been recruited and assessed, an interim analysis will also be conducted and presented to the DSMB, for which the p-value thresholds for stopping the study for superiority or futility will be 0.003 and 0.72, respectively. The p-value used at the end of the study with full enrollment will be 0.049, preserving an experimentwise 2-sided alpha level of 0.05. These stopping thresholds are based on an O'Brien-Fleming alpha spending function. For an additional level of safety oversight, the PI will place enrollment on temporary hold if 1 year mortality exceeds 35.5% and the DSMB will be asked to provide an expedited data safety review, concluding with next step recommendations. All analyses will be conducted in SAS v9.2 (Cary, NC).

Multiple correlation analyses will be performed between the inflammatory markers and other continuous outcome measures, such as fluid balance, inotropic score and hemodynamic variables. An assessment will also be made of the association between the inflammatory markers and categorical variables, such as the composite morbidity-mortality outcome and its components. Analyzed safety variables will include all reported adverse events, the incidence of acute renal injury and postoperative creatinine, hyperglycemia and infection.

12.11 Reporting Deviations from Original Statistical Plan

The principal features of the study design and of the plan for statistical analysis of the data are outlined in this protocol and in the subsequent Statistical Analysis Plan (SAP). Any changes in these principal features will require a protocol or an SAP amendment, which would be subject to review by the independent DSMB, the study sponsor, and the health authorities. These changes will be described in the final report as appropriate.

13 SOURCE DATA

13.1 Identifying Source Data

The investigator is required to keep accurate records to ensure that the conduct of the study is fully documented. The results of all clinical and clinical laboratory evaluations will be maintained in the participant's medical records and the data will be transferred to clinical CRFs. Source data is any source from which the study data is first found. Source data is accompanied by the person making the entry with a date of the entry, or a time date stamp and the signature of the persons making the entry (either computer generated signatures or other means to track back the entry person).

13.2 Permitting Access to Source Data

The investigational site participating in this study will maintain the highest degree of confidentiality permitted for the clinical and research information obtained from the participants in this clinical trial. Medical and research records should be maintained at each site in the strictest confidence. However, as a part of the quality assurance and legal responsibilities of an investigation, the investigational site must permit authorized representatives of the sponsor(s) and health authorities to examine (and when required by applicable law, to copy) clinical records for the purpose of quality assurance reviews, audits, and evaluations of the study safety and progress. Unless required by the laws that permit copying of records, only the coded identity associated with documents or with other participant data may be copied (and all personally identifying information must be obscured). Authorized representatives as noted above are bound to maintain the strict confidentiality of medical and research information that is linked to identified individuals. The investigational site will normally be notified before auditing visits occur.

The database will be dedicated solely for use by this study protocol and will be password protected. Case report forms will be kept in a secure file within the Department of Pediatric Cardiology. Data files will be password protected. Personal identification information will only be kept by persons directly involved with the study and then only used for study protocol follow-up and safety monitoring.

14 QUALITY CONTROL AND QUALITY ASSURANCE

The investigator is required to keep accurate records to ensure that the conduct of the study is fully documented. All participating clinicians and project staff will receive specific training as necessary from local physician investigators and the overall project manager before assuming any study-specific roles. Quality control of the study will be maintained by conference calls that will include all study investigators and staff. These calls will review the status of the study at each site, difficulties encountered with study procedures and adverse events, enrollment figures, retention figures, and completion and accuracy of data for each site. Additional training will be provided as necessary on an individual or study-wide basis. Copies of the informed consent document will be retained in the local study file.

Each participating site will obtain human subjects approval. As all sites will have a review by the Human Subjects Protection Committee/IRB of all protocol versions, consent versions and adverse events reports. The DSMB will formally review enrollment and safety biannually and as needed.

Since some sites might include research assessments in their medical records, the confidentiality of this information will be specified in the consent forms. Any materials considered solely for research purposes will be kept in locked study files in research areas or password-protected databases and not included in medical records. Access to these data will be limited to study personnel. All investigators and project staff will maintain current human subjects training. No identifying information will be reported in papers or presentations; data will be reported in aggregate.

Data will be entered locally at each site into a Web-based database using the assigned study ID, participant initials and date of birth. This database will incorporate the latest technology in Web-based data entry, data validation, automatic user authentication and feedback, and security. Each site will maintain a separate file linking a patient's identity to his or her study ID.

The NHLBI is responsible for regularly reviewing the conduct of the trial, for verifying adherence to the protocol, and for confirming the completeness, consistency, and accuracy of all documented data.

14.1 Data Monitoring Plan

The data will be verified by a series of computerized edit checks, and all relevant data queries will be resolved regularly and the site investigators will audit 10% of the medical records reviewed to assess data quality. All discrepancies will be reviewed, and any resulting queries will be resolved with the investigator and amended in the database. All elements of data entry (i.e., time, date, verbatim text, and the name of the person performing the data entry) will be recorded in an electronic audit trail to allow all data changes in the database to be monitored and maintained in accordance with federal regulations.

Some missing data are inevitable in any clinical study. The study will make every effort to minimize missing data through rigorous study procedures.

15 ETHICAL CONSIDERATIONS AND COMPLIANCE WITH GOOD CLINICAL PRACTICE

15.1 Statement of Compliance

This clinical study will be conducted using good clinical practice (GCP), as delineated in *Guidance for Industry: E6 Good Clinical Practice Consolidated Guidance*¹, and according to the criteria specified in this study protocol. Before study initiation, the protocol and the informed consent documents will be reviewed and approved by an appropriate EC or IRB. Any amendments to the protocol or to the consent materials must also be approved before they are implemented.

15.2 Informed Consent and Assent

The informed consent form is a means of providing information about the trial to a prospective participant's parent(s)/LAR and allows for an informed decision about participation in the study. All participants (or parent(s)/LAR) must read, sign, and date a consent form before entering the study, taking study drug, or undergoing any study-specific procedures. Consent materials for participants who do not speak or read English must be translated into the participants' appropriate language.

The informed consent form must be revised whenever important new safety information is available, whenever the protocol is amended, and/or whenever any new information becomes available that may affect participation in the trial.

A copy of the informed consent will be given to a prospective parent(s)/LAR for review. The attending physician will review the consent and answer questions. The prospective subject's parent(s)/LAR will be told that being in the trial is voluntary and that he or she may withdraw from the study at any time, for any reason.

